#### 4.4.1.3 SAEs

##### 4.4.1.3.1 Last Vaccination

Last vaccination will be computed using the same methodology as for unsolicited non-serious AEs described in Section 4.4.1.2.2.

##### 4.4.1.3.2 Time of Onset

Time of onset will be computed using the same methodology as for unsolicited non-serious AEs described in Section 4.4.1.2.3.

SAEs will be analyzed throughout the study using the following periods:

- Within 28 days after each/any injection
- During the study (i.e., all SAEs occurred during the study)

An SAE with missing time of onset will be considered to have occurred after the vaccination indicated by the visit number, so will be included in these tables.

Note: SAEs that occurred before vaccination (negative time of onset) will not be included in analysis, but will be listed separately.

Note for SAEs: Elapsed time from last vaccination recorded will be calculated if the SAE occurred within 24 hours of vaccination.

#### **4.4.1.3.3 Duration**

Duration will be computed using the same methodology as for unsolicited non-serious AEs described in Section 4.4.1.2.4 .

#### **4.4.1.4 Other Safety Endpoints**

##### **4.4.1.4.1 Action Taken**

This information will not be included in the analysis, but will be listed separately. No derivation or imputation will be done.

##### **4.4.1.4.2 Seriousness**

This information will be summarized as collected. No derivation or imputation will be done.

##### **4.4.1.4.3 Outcome**

This information will be summarized as collected. No derivation or imputation will be done.

##### **4.4.1.4.4 Causality**

This information will be summarized as collected. Missing causality (relationship) will be handled as described in Section 5.3.1.2.

##### **4.4.1.4.5 AEs Leading to Study Discontinuation**

A flag is available in the clinical database for all AEs in order to identify AEs leading to discontinuation.

##### **4.4.1.4.6 AEs of Special Interest (AESIs)**

The following serious AESIs (reported as SAEs) will be considered:

- Serious hypersensitivity/allergic reactions occurring in all subjects within 7 days after vaccination
- Serious viscerotropic disease occurring in all subjects within 30 days after vaccination
- Serious neurotropic disease occurring in all subjects within 30 days after vaccination
- Serious dengue disease requiring hospitalization occurring in all subjects at any time during the study

The following non-serious AESI will be considered:

- Hypersensitivity/allergic reactions occurring in all subjects within 7 days after vaccination

#### 4.4.2 Immunogenicity

##### 4.4.2.1 Computed Values for Analysis

For the computation of GMTs, any titer reported as < the lower limit of quantitation (LLOQ) will be converted to a value of  $\frac{1}{2}$  LLOQ.

While a single approach will be used for GMTs, two different approaches for geometric mean of the titer ratios [GMTR] will be applied:

- For CYD dengue vaccine, < LLOQ will be converted to  $\frac{1}{2}$  LLOQ for a numerator and < LLOQ will be converted to LLOQ for a denominator
- For Gardasil, < LLOQ will be converted to  $\frac{1}{2}$  LLOQ.

##### 4.4.2.2 CYD Dengue vaccine Seropositivity and other thresholds

Several thresholds of interest will be used to evaluate the immunogenicity of CYD Dengue vaccine.

For each threshold applied on each serotype, the derived indicator will be "Yes" for that serotype if the computed value meets the threshold, otherwise indicator will be "No".

At baseline and 28 days after each dose of CYD Dengue vaccine, the thresholds considered are:

- Seropositivity: titer  $\geq 10$  (1/dil)
- Distribution rates of titers against each serotype according to the following predefined thresholds (1/dil):  $<10, \geq 10, \geq 20, \geq 30, \geq 40, \geq 60, \geq 80, \geq 100, \geq 120, \geq 140, \geq 160, \geq 180, \geq 200, \geq 220, \geq 240, \geq 260, \geq 280, \geq 300, \geq 320, \geq 340, \geq 360, \geq 400, \geq 640$  and  $\geq 1280$ .

---

 A hospitalized subject is any subject admitted to hospital with bed attribution or any healthcare institution and requiring in-patient care.

#### **4.4.2.3 CYD Dengue vaccine Seropositivity against at least X serotype(s)**

The criteria below will be computed for each subject and visit as soon as at least one of the four dengue serotype result is different from missing or not-reportable (“NR”) (i.e. coded no result in the serology database):

- Number and percentage of subjects with antibody titer  $\geq 10$  (1/dil) against at least 1, 2, 3, or the 4 serotypes with the parental dengue virus strains.

Titer(s)  $\geq 10$  (1/dil) for at least X serotype(s) with parental dengue virus strains is computed as a Yes/No/Missing variable (note: in the case no titer is available the variable will be missing). If at least X among the 4 serotypes titers meet the threshold then the variable is derived to “Yes”, otherwise if at least one titer is available and does not meet the threshold the variable is derived to “No”. For the percentage calculation, all the subjects with at least one titer available regardless of the serotype will be considered in the denominator.

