9.2 Secondary Endpoints and Assessment Methods

9.2.1 Immunogenicity

9.2.1.1 Immunogenicity Endpoints

Gardasil immunogenicity:

• Seroconversion against each Gardasil HPV antigen (HPV-6, HPV-11, HPV-16, HPV-18) 28 days after each dose of Gardasil

Seroconversion is defined as changing serostatus from seronegative at baseline to seropositive (> lower limit of quantitation [LLOQ] of the assay) or \geq 4-fold rise in Ab titer if seropositive at baseline.

• Ab levels (measured by cLIA) against each Gardasil HPV antigen (HPV-6, HPV-11, HPV-16, HPV-18) at baseline and after each dose of Gardasil

CYD dengue vaccine immunogenicity:

• Neutralizing Ab titers against each of the four parental dengue virus serotypes of the CYD dengue vaccine as determined by PRNT50 at baseline and after each dose of the CYD dengue vaccine

- Neutralizing Ab titers ≥ 10 (1/dil) against each of the four and against at least 1, 2, 3, or 4 parental dengue virus serotypes of the CYD dengue vaccine as determined by PRNT50at baseline and after each dose of the CYD dengue vaccine
- Neutralizing Ab titers ≥ different titer thresholds (1/dil) against each parental dengue virus serotype of the CYD dengue vaccine as determined by PRNT50 at baseline and after each dose of the CYD dengue vaccine

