### 5.3.2 Immunogenicity

For the computation of GMTs, any titer reported as < LLOQ will be converted to a value of 1/2 LLOQ.

While a single approach was used for GMTs, two different approaches for GMT ratios were applied:

- For Gardasil, < LLOQ will be converted to 1/2 LLOQ
- For CYD dengue vaccine, < LLOQ will be converted to 1/2 LLOQ for a numerator and < LLOQ will be converted to LLOQ for a denominator

Missing data will not be imputed. No test or search for outliers will be performed.

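### SAP 4.4.2.3 counts subjects with incomplete PRNT results as non-responders in the four-serotype seropositivity rate, which lowers that descriptive rate whenever partial results occur

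*SAP*

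**What the plan says.** Protocol 9.2.1.1 lists as a secondary endpoint a neutralizing titer of at least 10 (1/dil) "against each of the four and against at least 1, 2, 3, or 4 parental dengue virus serotypes of the CYD dengue vaccine", at baseline and after each CYD dose.

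SAP 4.4.2.3 derives the at-least-X variable in three steps and then fixes the denominator:

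- Yes: "If at least X among the 4 serotypes titers meet the threshold then the variable is derived to" Yes.
- No: "otherwise if at least one titer is available and does not meet the threshold the variable is derived to" No.
- Missing: "in the case no titer is available the variable will be missing".
- Denominator: "For the percentage calculation, all the subjects with at least one titer available regardless of the serotype will be considered in the denominator".

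SAP 5.3.2 gives the general rule for immunogenicity data: "Missing data will not be imputed". SAP 5.2.5 assigns this endpoint to the FAS by baseline dengue status, and SAP 5.2.1 sets no serology condition for entering the FAS.

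**The concern.** A rule that counts X of four results has to say what happens when fewer than four results exist and those in hand do not settle the count. SAP 4.4.2.3 anticipates partial results, because it starts the derivation as soon as one serotype result is neither missing nor NR. It does not give unsettled patterns an outcome of their own.

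At X = 4, take titers of 50, 80, 40 and NR. Yes is impossible with three reported titers. No, read literally, needs a reported titer below threshold, and there is none. Missing is stated only for the case with no titer at all. The subject is unclassified, yet the denominator sentence includes the subject.

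At stake is the interpretation of the four-serotype response rate. It would mix antibody response with completeness of the assay results, and the error goes in one direction. The FAS does not screen out partial results, and no sensitivity analysis is planned that would show the effect.

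**Working it through.** The documents state no four-serotype rate and no PRNT missing or NR rate, so there is no planned figure to reproduce. The check has two parts.

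**1. Apply the rule to every partial pattern.** P is a reported titer of at least 10, N a reported titer below 10, M missing or NR. An asterisk marks a result that is not Yes although X of 4 is still attainable.

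| Pattern | X = 1 | X = 2 | X = 3 | X = 4 |
|---|---|---|---|---|
| PPPM | Yes | Yes | Yes | unclassified* |
| PPMM | Yes | Yes | unclassified* | unclassified* |
| PMMM | Yes | unclassified* | unclassified* | unclassified* |
| PPNM | Yes | Yes | No* | No |
| PNNM | Yes | No* | No | No |
| PNMM | Yes | No* | No* | No |
| NNNM | No* | No | No | No |
| NNMM | No* | No* | No | No |
| NMMM | No* | No* | No* | No |

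Every pattern in the table enters the denominator. Each asterisked cell contributes nothing to the numerator although the complete result might have been Yes. The reported rate can therefore never exceed the full-data rate in the same subjects.

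**2. Size at X = 4.** Let p4 be the true four-serotype rate and m the probability that any one serotype titer is missing or NR, independent of titer and across serotypes. The numerator needs all four reported and all at least 10; the denominator needs at least one reported:

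expected reported rate = p4 × (1 − m)^4 / (1 − m^4)

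With p4 = 90% (assumed):

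| m (assumed) | Subjects not complete, 1 − (1 − m)^4 | Reported rate | Bias (points) |
|---|---|---|---|
| 0.5% | 2.0% | 88.2% | −1.8 |
| 1% | 3.9% | 86.5% | −3.5 (unrounded −3.55) |
| 2% | 7.8% | 83.0% | −7.0 |
| 5% | 18.5% | 73.3% | −16.7 |

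Equivalently, if a share q of the denominator lacks a titer, the bias is −q × p4. At p4 = 90% that is −0.9, −1.8, −4.5 and −9.0 points for q = 1%, 2%, 5% and 10%. At q = 0 it is zero.

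**3. Other values of X.** A simulation of 2,000,000 subjects assumed 95% seropositive per serotype, independent across serotypes, and 2% missing per serotype:

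| X | True | SAP rule | Subjects with all four titers |
|---|---|---|---|
| 4 | 81.5% | 75.1% | 81.5% |
| 3 | 98.6% | 97.4% | 98.6% |
| 2 | 99.95% | 99.87% | 99.95% |
| 1 | 100% | 100% | 100% |

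**4. A count example.** Take 121 subjects, of whom 109 are truly positive for all four serotypes, and let 6 of those 109 have one NR titer. The SAP rule reports 103/121 = 85.1%, against 109/121 = 90.1% with full data.

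**The case against.** Several points on the other side stand.

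- A reader might infer that any unreported titer counts as a vaccine failure. The rule does not do that. For X below 4 the subject is still Yes if enough reported titers reach 10. At X = 4, No is correct whenever a reported titer is below 10, whatever the absent one would have shown. At baseline the word failure does not apply at all.
- A reader might extend the point to SAP 4.4.2.2, where the per-serotype indicator is Yes "if the computed value meets the threshold, otherwise indicator will be" No. A missing titer has no computed value, SAP 5.3.2 rules out imputation, and that section states no denominator. At most it lacks a detail.
- A reader might turn the table into a spurious group difference, for example 90.0 − 83.0 = 7.0 points with 2% NR in one group and none in the other. Nothing in the documents suggests that NR differs between the randomized groups.
- Independent NR per serotype is an unfavourable assumption. If too little serum loses the whole sample, all four titers are absent, the subject is Missing and excluded, and no bias arises.
- SAP 5.3.2 is about titer values, and SAP 4.4.2.3 fills in no titer. The two sit uneasily together, but this is not a flat contradiction. The rule is also pre-specified, uses one denominator for all X, and errs against the vaccine.
- SAP 5.1.2.1 tests no hypothesis on CYD secondary objectives, and serotype-specific GMTs and distribution curves are reported in any case.

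These points limit the scope and consequence. They do not supply an outcome for the unclassified X = 4 pattern, and they do not change the denominator sentence, which determines the percentage on either reading of the No clause.

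**Conclusion.** The point holds for the four-serotype rate. SAP 4.4.2.3 leaves one type of partial result unclassified and counts it as non-response, so the reported rate is too low whenever such results occur. The direction follows from the wording. The size does not: it rests on an assumed true rate of 90%, assumed NR rates and NR unrelated to titer, under which the loss runs from about 1.8 points at 0.5% NR per serotype to 16.7 points at 5%. The effect at X = 3 is smaller (1.2 points in the simulation) and at X = 1 and X = 2 negligible under the simulated response rates.

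The co-primary GMT comparisons, the seroconversion test for Gardasil and the power tables do not use this variable. The change is worth making because the endpoint is named in the protocol, the programmer would otherwise have to guess, and the repair is small.

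**What to change.** In SAP 4.4.2.3, compute the at-least-X percentages among subjects with all four serotype titers reported at that visit, and set the variable to Missing for everyone else. Report the number with partial results by group and visit. As a sensitivity display, show a best/worst-case range in which all undetermined subjects are taken first as Yes and then as No.

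A rule that keeps settled subjects and drops only unsettled ones is tempting but should not be used, because whether a subject is settled depends on the response:

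- At X = 4 one titer below 10 settles No, so the rate stays low. In the count example, dropping the 6 unsettled subjects gives 103/115 = 89.6%, against 90.1%.
- At X = 1 one titer of at least 10 settles Yes, so the rate rises. If half the subjects are positive to all four serotypes and half to none, 2% NR gives 0.5 / (0.5 + 0.5 × 0.98^4) = 52.0% instead of 50%.

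The complete-titer denominator is unbiased when NR is unrelated to titer; the range covers the case where it is not.

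The cost is one sentence of SAP text, a line of derivation code and a slightly smaller denominator. At baseline, a subject with partial results could be Missing here while SAP 4.4.5 still assigns a dengue status, so a footnote should explain the difference in counts.

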#### **4.4.2.4 Gardasil Seroconversion**

Seroconversion 28 days after each dose is defined as changing serostatus from seronegative at baseline to seropositive ( $>$  LLOQ of the assay) or  $\geq 4$ -fold rise in Ab titer if seropositive at baseline.

#### **4.4.3 Efficacy**

Not applicable.

#### **4.4.4 Derived Other Variables**

##### **4.4.4.1 Age for Demographics**

The age of a subject in the study is the calendar age.

##### **4.4.4.2 Duration of the Study**

The duration of the study is computed in days as follows:

Latest date of all subjects (termination date, last visit date, date of last contact) – earliest date of all subjects (date of visit V01) +1.

##### **4.4.4.3 Subject Duration**

The duration of a subject participation in the study is computed as follows:

Maximum (Visit dates, Termination date, Follow-up date, Last contact date) – V01 date + 1.

#### **4.4.5 Baseline Dengue status**

The dengue serostatus at baseline is defined as the presence of Abs against at least one dengue serotype in the baseline sample (by dengue 50% plaque reduction neutralization test [PRNT50]) in

the blood sample collected at V01 for group 1 and at V02 for group 2. The baseline dengue status will be derived for each subject as follows:

- Dengue immune subjects (seropositive) at baseline are defined as those subjects with titers  $\geq 10$  (1/dil) for at least one serotype with the parental dengue virus strain.
- Dengue non-immune subjects (seronegative) at baseline are defined as those subjects with titers  $< 10$  (1/dil) (not quantified) for all serotypes with parental dengue virus strains with available and “valid” results (i.e. not coded “NR”) in the serology database.
- Otherwise the baseline status will be classified as undetermined and subjects will have their dengue baseline status derived as non-immune.

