9.1 Primary Endpoints and Assessment Methods

9.1.1 Immunogenicity

9.1.1.1 Immunogenicity Endpoints

The primary endpoint(s) for the evaluation of immunogenicity are:

Gardasil immunogenicity

• Ab levels (measured by [cLIA]) against each Gardasil HPV antigen (HPV-6, HPV-11, HPV-16, HPV-18) 28 days after the last dose of Gardasil

CYD dengue vaccine immunogenicity

• Neutralizing Ab levels (measured by dengue plaque reduction neutralization test [PRNT50]) against each of the four parental dengue virus serotypes of the CYD dengue vaccine (1, 2, 3, 4) 28 days after the last dose of the CYD dengue vaccine

Definition of dengue serostatus

The dengue serostatus at baseline is defined as the presence of Abs against at least one dengue serotype in the baseline sample (by dengue 50% plaque reduction neutralization test [PRNT50) in the blood sample collected at V01 (BL1) from all subjects. The baseline dengue status variable will be calculated for each subject as follows:

- Dengue immune subjects (dengue exposed) at baseline are defined as those subjects with titers $\geq 10 (1/dil)$ for at least one serotype with the parental dengue virus strain
- Dengue non-immune subjects (dengue unexposed) at baseline are defined as those subjects with titers <10 (1/dil) (not quantified) for all serotypes with parental dengue virus strains with available "valid" results (i.e. different from missing or "NR")

The baseline dengue status will be set to missing when the titer for any serotypes with parental dengue virus is either missing or not quantified (except if all are not quantified in which case the dengue status is non-immune)."

In case of limited serum volume, the priority will be given to the testing of the dengue serostatus at baseline testing over the other testing (HPV immunogenicity post Gardasil may be not performed if not enough blood volume).

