##### ***Descriptive analysis on Gardasil and CYD dengue vaccine immunogenicity***

No hypotheses will be tested.

Immunogenicity point estimates and their 95% CI will be presented for each and any group, at baseline and after each dose of Gardasil and CYD dengue vaccine.

A complementary analysis on CYD dengue vaccine immunogenicity after each dose will be conducted for each and any group according to the dengue status at baseline (dengue immune, dengue non-immune, and all subjects).

The 95% CIs will be calculated using:

- The normal approximate method for GMTs and GMTRs  
Assuming that  $\log_{10}$  transformation of the titers / data follows a normal distribution, at first, the mean and the 95% CI will be calculated on  $\log_{10}$  (titers / data) using the usual calculation for normal distribution (using Student’s t distribution with  $n-1$  degree of freedom), then antilog transformations will be applied to the results of calculations, in order to provide geometric means (GMs) and their 95% CI.
- The exact binomial distribution for single proportions (Clopper-Pearson’s method, quoted by Newcombe)

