##### ***Safety***

All analyses will be descriptive; no hypotheses will be tested. Safety will be assessed for all subjects and for immune subjects after each and any dose of Gardasil and CYD Dengue vaccine. Moreover, a complementary analysis will be performed for each dose of CYD dengue vaccine, for each and any group, on non-immune subjects.

As there are differences in the intensity considered for measurable reactions depending on ages of subjects, a complementary analysis will be performed according to the following age groups: 9-11 years and 12 to 13 years.

For the main parameters, 95% CIs of point estimates will be calculated using the normal approximation for quantitative data and the exact binomial distribution (Clopper-Pearson method, quoted by Newcombe) for single proportions.

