### 5.2.1 Full Analysis Set

The Full Analysis Set (FAS) is defined as the subset of subjects who received at least one dose of the study vaccines.

Subjects will be analyzed by baseline dengue status and the vaccine treatment group to which they were randomized.

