#### **5.2.3 Safety Analysis Set**

The SafAS is defined as those subjects who have received at least one dose of the study vaccines. All subjects will have their safety analyzed after each dose according to the vaccine they actually received, and after any dose according to the vaccine received at first dose.

The safety data will also be presented separately for dengue immune, non-immune / undetermined subjects.

Safety data recorded for a vaccine received out of the protocol design will be excluded from the analysis (and listed separately).

Note: Subject will be included in the “any dose” analysis according to the 1st dose received that corresponds to a protocol group.

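### The SAP counts subjects of undetermined baseline dengue status as non-immune where the protocol sets them to missing, so the descriptive non-immune results can include subjects never shown to be seronegative

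*SAP*

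**What the plan says.** Both documents call a subject immune at baseline if at least one serotype has a titer of 10 or more, and non-immune if all titers are below 10. They differ on everyone else.

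- **Protocol 9.1.1.1:** "The baseline dengue status will be set to missing when the titer for any serotypes with parental dengue virus is either missing or not quantified", with one exception: "except if all are not quantified in which case the dengue status is non-immune".
- **SAP 4.4.5:** "Otherwise the baseline status will be classified as undetermined and subjects will have their dengue baseline status derived as non-immune".

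The SAP then uses the status in several places, with different labels.

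- **SAP 5.2.1 (FAS):** "Subjects will be analyzed by baseline dengue status and the vaccine treatment group to which they were randomized".
- **SAP 5.2.3 (safety set):** "The safety data will also be presented separately for dengue immune, non-immune / undetermined subjects".
- **SAP 5.1.2.2 (safety):** "a complementary analysis will be performed for each dose of CYD dengue vaccine, for each and any group, on non-immune subjects".
- **SAP 5.1.2.2 (dengue immunogenicity):** the strata are "dengue immune, dengue non-immune, and all subjects".

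SAP 5.7, which records changes to the planned analyses, mentions the restriction of non-inferiority testing to immune subjects and the reporting by baseline status. It does not mention the recoding.

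**The concern.** Amendment 1 exists because the IDMC concluded that the vaccine acts differently in exposed and unexposed subjects. That is why safety and immunogenicity are now reported by serostatus. A non-immune column is useful only if its subjects were shown to be seronegative. Under SAP 4.4.5 a subject with no usable baseline result enters that column by default.

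Three things would follow. Any contrast in event risk between the strata would shrink towards no difference. Post-dose dengue GMTs labelled non-immune could include titers from subjects who were immune at the start. And a reader of the 5.1.2.2 tables could not tell that untested subjects were in them.

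**Working it through.** **1. What the two rules do, case by case**

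| Baseline titers | Protocol 9.1.1.1 | SAP 4.4.5 |
|---|---|---|
| At least one titer of 10 or more | Immune (but see step 5) | Immune |
| All four valid, all below 10 | Non-immune | Non-immune |
| Some below 10, the rest missing or not reportable | Missing | Non-immune, by the second bullet or by the catch-all |
| No valid result | Missing | Undetermined, then non-immune |

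The SAP's second bullet can be read as needing all four results, or only those that are valid. The outcome is the same either way: anyone without a titer of 10 or more ends as non-immune.

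**2. Can the last two rows be populated?** Yes. A footnote in Protocol 5.1.4 lets a subject whose blood could not be drawn be vaccinated all the same. Both documents also provide for not-reportable results.

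**3. Which outputs are affected?**

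- *Non-inferiority tests:* none. SAP 5.1 tests in immune subjects, both per-protocol sets exclude non-immune subjects (SAP 5.2.2), and the FAS confirmation is in immune subjects (SAP 5.2.5).
- *Subject with no baseline result who received CYD vaccine:* enters the per-CYD-dose non-immune safety tables and, through post-dose titers, the non-immune dengue GMTs.
- *Group 2 subject lost between V01 and V02:* the baseline dengue sample and the first CYD dose are both at V02, so this subject has neither. The subject is in the safety set and in the SAP's FAS, each of which needs one dose of study vaccine. The effect is confined to the Gardasil, any-dose and throughout-study denominators, such as hospitalized VCD (a percentage of subjects in SAP Table 5.1). The per-CYD-dose tables and the dengue GMTs are untouched, since missing titers are not imputed (SAP 5.3.2).

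**4. Size**

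No figure in the documents depends on this rule, so there is none to reproduce. The only input they give is N = 528 (SAP 5.5). The number undetermined, u, and the seroprevalence, s, are assumed, and undetermined subjects are taken to be immune with probability s.

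- True non-immune with a valid result: n0 = (1 − s)(N − u)
- Truly immune share of the reported non-immune stratum: c = u·s / (n0 + u)

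Results:

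- u = 10, s = 0.8: n0 = 0.2 × 518 = 103.6; c = 8 / 113.6 = 7.0%
- u = 3, s = 0.5: n0 = 0.5 × 525 = 262.5; c = 1.5 / 265.5 = 0.6%

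Over a wider range, with u from 0.5% to 5% of 528 (about 3 to 26 subjects), c runs from 0.5% to 4.8% at s = 0.5 and from 4.3% to 31% at s = 0.9.

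If the true risk ratio, non-immune to immune, were 2 (assumed), the reported ratio would be 2(1 − c) + c = 2 − c. That is 1.93 for c = 7.0% and 1.99 for c = 0.6%. Over the wider range it is 1.95 to 1.995 at s = 0.5 and 1.69 to 1.96 at s = 0.9.

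**5. The protocol rule also needs repair.** Read literally, a single titer that is not quantified sets the status to missing even when another is 10 or more, against the protocol's own definition of immune. It also places the baseline sample at V01 for all subjects, while Protocol Table 7.1 has no dengue draw at V01 in Group 2 and the SAP uses V02 for that group.

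**The case against.** The strongest reply is that this is a labelling matter of small size, and much of that stands.

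- **The category is probably small.** Failed draws are to be reattempted (Protocol 5.1.4), serostatus testing has priority when serum is short (Protocol 9.1.1.1), and the SAP Introduction reports that all vaccinated subjects were told their baseline serostatus.
- **The pooling is partly disclosed.** SAP 5.2.3 names undetermined subjects in its label. That does not reach the 5.1.2.2 strata, and a pooled column cannot be separated afterwards.
- **The protocol is not a clean benchmark.** True (step 5), and the SAP had reason to depart from it. Those faults do not justify coding an unknown status as non-immune.
- **Pooling follows the treatment path.** Protocol 1.4 reserves further CYD doses for subjects assessed as exposed, so undetermined subjects share the shortened course of non-immune subjects. That could justify a pooled safety display, not an unlabelled one.

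A reader might also infer more than the documents support:

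- *That the design loads the error onto Group 2.* The later sample does create a route that Group 1 lacks, but such subjects reach only the denominators in step 3. Protocol 5.1.3 also says that at Amendment 1 all subjects except 8 had received a second CYD dose, which suggests few early losses even if it counts only active subjects.
- *That undetermined means no result at all.* It can include partly tested subjects whose valid titers are all below 10. They are more likely to be non-immune, so applying s to them overstates c.
- *That 11% or 20% of the stratum could be immune with 10 undetermined at 80% seroprevalence.* Those shares need n0 = 60 (8/70) or n0 = 30 (8/40). On 528 subjects that seroprevalence implies about 104, hence 7%.
- *That the trial's answer on seronegative risk is at stake.* Safety is descriptive, follow-up ends 6 months after the last injection, and there is no unvaccinated control.

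**Conclusion.** The concern holds for the descriptive serostatus strata and no further. The SAP and protocol classify the same subjects differently, the change is undeclared, and the SAP's own labels disagree. No confirmatory conclusion changes.

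The size cannot be settled from the documents. It rests on an assumed number undetermined, an assumed seroprevalence, and the assumption that undetermined subjects are immune at the population rate. On those terms the truly immune share of the reported non-immune stratum is about 0.6% to 7% in the two worked cases. It becomes large only if both the undetermined count and the seroprevalence are high. The count of undetermined subjects would show which case applies, and the SAP does not ask for it. The correction is worth making because it costs so little.

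**What to change.** - In SAP 4.4.5, keep undetermined as its own category: no valid result, or incomplete results with no titer of 10 or more. Count it in the all-subjects tables but in neither stratum. If a two-way split is preferred, show non-immune with and without it.
- Report the number undetermined by group and reason (no sample, not reportable, left before the baseline dengue sample).
- Use the same labels in SAP 5.1.2.2 and 5.2.3.
- State in SAP 5.2.2 that undetermined subjects are also excluded from both per-protocol sets. The present exclusion names only non-immune subjects, so without this line the new category would leave their place unclear.
- Reconcile with Protocol 9.1.1.1, correcting its wording on any titer that is not quantified and its use of V01 as baseline for all subjects.
- List the change in SAP 5.7.

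The cost is a few lines of SAP text, one extra column or row, and a slightly smaller non-immune stratum. None of this bears on who receives vaccine.
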